The overarching goal of this proposal is to a) assess the feasibility and preliminary validity of **home-based delivery of TeleNP** to patients with suspected AD, referred for cognitive assessments in a Neurology Clinic; and b) elucidate whether TeleNP is equivalent to face-to-face evaluation (FF) for diagnostic adjudication of atypical versus typical AD. To accomplish these goals, we will conduct a **pilot clinical trial** of two testing modalities, TeleNP versus FF, for delivery of neuropsychological evaluations. Neurologist-referred patients with typical (i.e., memory-predominant; n=40) and atypical (i.e., complex and/or non-memory predominant; n=40) presentations of *possible* AD will be enrolled in the study. Care partners of participants will also be consented to the study and included in stakeholder surveys/interviews. Using a cross-over design, all participants will undergo evaluations (clinical interview + Core Battery of cognitive tests) in both modalities, approximately 4-6 weeks apart to account for potential practice effects. Although all participants will be referred due to suspected AD, the neuropsychologist will be blinded to the specific diagnosis (i.e. typical versus atypical) from the neurologist. The Core Battery will include measures of memory, executive, visuospatial, and language functions. To further minimize practice effects, alternate assessment forms will be implemented and order of test forms will be counterbalanced. Some tests are not readily adaptable to video-based delivery due to tactile/physical stimuli; as such, we will assess whether a Flexible Assessment (i.e., option to include additional tests, after completion of Core Battery) in the FF modality alters diagnostic conclusions. Finally, in an exploratory aim, we will identify stakeholder perspectives of TeleNP that inform pragmatic implementation of remote neuropsychological evaluations. Our Aims are:

Aim 1: Determine the validity of home-based video administration of neuropsychological tests (TeleNP) for assessing AD. 1a: Are cognitive test results equivalent across TeleNP and FF conditions in patients with suspected AD? 1b. Is this equivalence consistent across referral diagnoses (i.e., Typical vs. Atypical AD)? *This Aim will test the validity of cognitive measures assessed with TeleNP and determine whether the validity of TeleNP differs based on referral diagnosis.*

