IV. Research Methods

A. Description of Population to be Enrolled:

Clinical Trial Participants (Patients):

We will recruit 80 patients from the **UCH Memory Disorders Clinic** (considering possible screen fails, up to 150 may ultimately be recruited). To understand the feasibility and preliminary validity of TeleNP, we will enroll 1) 40 adults with suspected **typical** AD (i.e., memory-predominant) and 2) 40 adults wherein AD is on the neurologist's diagnostic differential, but the presentation is **atypical** (i.e., complex/non-memory predominant presentations). The typical and atypical AD groups will range in severity from MCI to mild dementia (based on referring neurologist's determination); this is consistent with current conceptualizations of AD, in which clinical syndrome (AD) is distinct from severity of presentation (MCI; dementia).^{1, 2}

All participants with suspected AD will be referred by neurologists. Our specific inclusion/exclusion criteria will be:

Inclusion criteria:

Eligible participants will be adults \geq 60 years and <90 years who are undergoing evaluation for possible AD and whose severity ranges from MCI to mild dementia. Of note, we are excluding individuals aged 90 and over, as recent studies suggest that individuals in the oldest-old category differ from other individuals with MCI or dementia in terms of risk factors for AD and prevalence of non-AD pathologies.²¹⁻²³ In addition, limited age-referenced normative data for neuropsychological tests are available for individuals 90 and over, which impacts our ability to address Aims 1 and 2.

Eligible participants must carry a diagnosis of either suspected typical AD or atypical AD, based on the referring neurologist's diagnosis.

- Typical AD: Defined as a memory-predominant presentation of AD.
- Atypical/Complex AD: Defined as a complex (i.e., AD is under consideration, but other diagnoses may be included in neurologist's differential diagnosis) and/or non-memory predominant phenotype of AD.

Both patient groups will be based solely on the neurologist's clinical diagnosis after the initial Neurology visit, and in the absence of formal neuropsychological test results, to minimize circularity.

Exclusion criteria:

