HIPAA privacy notification language will be incorporated into the informed consent document and will be signed by all participants prior to any procedures being carried out. Informed consent language will include key facts about the study, the study events, timeline, the study participant's role in the study, potential risks and benefits and highlight the fact that participation is completely voluntary and will be signed by all study participants. The informed consent/HIPAA form will specify that the database will receive and store all research data. Information regarding the purpose and procedures for this project will be given in both oral and written form. All study participants will be consented in privacy and will be given as much time as they need to read, discuss and ask questions about study events and their respective roles and participation in the study. They will be reassured that the same ethical and legal codes that govern medical practice

[figure not shown]
also apply to clinical research and they will be given the opportunity to ask questions and receive information regarding the goals and details of this study. If the Principal Investigator or Co-Investigators do not initially participate in the discussion, they will be available to answer questions prior to obtaining written informed consent/authorization.

Subjects may withdraw participation in the study at any time by calling, writing, or emailing the Principal Investigator or study coordinator. Subjects will be unable to withdraw data that has already been analyzed, presented, or published.

B. Study Design and Research Methods

Randomization, Intervention and Neuropsychological Assessment Methods

Study participants will undergo both modalities (FF; TeleNP), conducted 4-6 weeks apart (allowing for maximum of 90 days). Order of modality will be randomized at baseline using a computerized process through REDCap, developed by [name]. Similarly, assignment of supervising neuropsychologist will be randomized and counterbalanced across testing conditions. Our goal of using two neuropsychologists is to minimize bias; specifically, use of the same neuropsychologist for the same patient across both modalities would likely influence their interview approach and diagnostic adjudication due to recollection of the prior assessment.

Abbreviations and Terminology:

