--Participants' age, birthdate, sex, gender, education level (Years), race/ethnicity, prior occupation, etc. will be obtained. Participant's contact information and address will also be obtained to facilitate scheduling baseline and follow-up appointments.

Interview:

--Participant's symptom history will be documented on a standard data collection sheet during the interview portion.

Neuropsychological Testing, Core Battery (May not be given in its entirety):

- Cognitive/Mood Surveys:
 - Geriatric Depression Scale
- Cognitive Assessments:
 - Global:
 - MoCA, with alternate forms
 - Memory:
 - CVLT-II, with alternate forms
 - Benson Figure Recall / RBANS Figure Recall
 - Speed/Executive Functions:
 - Oral Trail Making Test
 - Oral Symbol Digit Modality
 - Digit Span, with alternate forms
 - Verbal Fluency, with alternate forms (FAS; BHR)
 - Color Word Inhibition
 - Language:
 - Sentence Repetition
 - Boston Naming Test-15 item, with alternate forms
 - Verbal Agility
 - WRAT Reading
 - Abbreviated Peabody Picture Vocabulary Test
 - Syntactic Comprehension
 - Visuospatial and Posterior Cortical Function
 - Judgment of Line Orientation (Short Form)
 - Benson Figure Copy / RBANS Figure Copy
 - Calculation Screen

Neuropsychological Testing, Flexible Assessment:

- Cognitive Assessments in addition to Core Battery (May not be administered in its entirety):
 - Grooved Pegboard
 - Clock Drawing Test
 - Rey-Osterrieth Complex Figure
 - BVMT
 - Navon Figures
 - Face Perception/Affect Naming
 - VOSP Number Localization
 - Design Fluency
 - Written Trail Making Test A & B

Surveys:

- 4-item measures of acceptability and feasibility
- 19-item modified UTAUT after TeleNP portion

Cognitive Composites, Neuropsychologist Diagnosis, and Interviews: See Outcome Measures Below

Data Collection for Care Partner Participants:

Demographics:

--Care partner's age, birthdate, sex, gender, education level (Years), race/ethnicity, prior occupation, etc. will be obtained. Participant's contact information and address will also be obtained to facilitate scheduling baseline and follow-up appointments.

Surveys:

- 4-item measures of acceptability and feasibility
- 19-item modified UTAUT after TeleNP portion

Interviews: See Outcome Measures Below

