Incorporation of Results into Clinical Care: Because the set battery used in the FF assessment uses validated tests that are normally used for these patients in clinical care, it is likely that patients in this study *will not* undergo a separate standard of care neuropsychological assessment. Therefore, a brief research overview of the results of the FF assessment will be provided to the referring neurologist and the participant after both conditions are complete (and posted to Epic Medical Record as a research note), for use in their clinical care. Based on a

national survey, the median time between neuropsychological assessment and completion of reports is 3 weeks; our proposed time is slightly longer than the median, but remains within an expected range for clinical reports.³¹ Of note, when considering the amount of time between referral and scheduled date of assessment in SOC (often on the order of months), our window will likely be shorter/faster than SOC given dedicate research time. If any safety, psychological or other signs of distress related to potential diagnosis of AD are noted during either assessment, appropriate referrals will be coordinated by Drs. [name] and [name]. Drs. [name] and [name] will coordinate with the neurologist to determine if prompt discussion of the first assessment is clinically prudent. The research note posted to Epic EMR will include a brief background/history, table of scores for FF condition, and summary/recommendations, consistent with standard of care approaches.

C. Outcome Measure(s):

Aim 1: Equivalence of Cognitive Test Results: *The goal of this Aim is to test the concurrent validity of cognitive measures across testing modalities and determine whether the test results differ based on referral diagnosis.* Z-scores will be calculated based on age-referenced normative data for each cognitive test (Table 1) in the Core Battery. For data reduction purposes, a mean z-score for each cognitive domain will be used (i.e., memory, executive functions, spatial abilities, language). This will allow us to address whether neuropsychological test results are equivalent across modality (i.e., FF vs. TeleNP) and whether complexity of referral impacts comparability of test results.

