F. Statistical Analysis Plan:

For **Aim 1**, we will adopt an equivalence testing framework. The null hypothesis is that there is an average difference of at least .5 SD units in the difference in the z-scores, where .5 SD defines a potentially clinically meaningful difference. The alternative hypothesis is that the mean of the

difference in the z-scores is zero. This is the reverse of standard statistical testing. We elected a .5 SD margin as an initial threshold for a clinically meaningful difference; the reason for this decision is that once an individual reaches a level deemed to be clinically significant impairment (e.g., mild impairment = -1.5 SD; moderate impairment =-2.0 SD), a change in .5 SD equates to a categorical difference in their overall severity rating. To conduct our equivalence test, we will compute the difference in the z-score between the FF and TeleNP conditions and compute the mean difference and a 90% confidence interval based on a t-test. This results in an equivalence test with an alpha=0.05. If the entirety of bounds of the 90% confidence interval are between (-.5SD, .5SD), then the two assessments will be considered equivalent. We will repeat this computation stratified by referring diagnosis (typical vs. atypical), and also by sex or race/ethnicity (white vs. non-White).

For **Aim 2**, we will compute a 3x3 table with the rows as TeleNP diagnosis and the columns as FF diagnosis to summarize the results. To assess the equivalence of TeleNP and FF for each condition we will create 3, 2x2 tables. For example, when assessing for differences in typical AD we will collapse over atypical AD and Not AD. Following prior work³⁵, we will compute the difference proportion of typical AD for the TeleNP and FF setting and construct a 90% confidence interval. A difference of proportions greater than 5% will be considered a clinically meaningful difference. If the 90% confidence interval is between (-5%,5%), then the two modalities will be considered equivalent. We will repeat this process for the two other neuropsychologist-determined categories (atypical AD, Not AD). We will conduct the same analyses, stratified by severity. We will assess whether the neuropsychologists' diagnosis is equivalent to the Flexible Assessment by repeating the above analysis using the Flexible vs FF diagnosis (i.e., diagnosis reported prior to initiating Flexible Assessment).

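### Aim 1 has no provision for floor or ceiling scores, which shrink a true modality effect toward zero and so favour declaring equivalence

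*Combined protocol and SAP*

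**What the plan says.** Section F (Statistical Analysis Plan) states the Aim 1 null on the z-score scale: "The null hypothesis is that there is an average difference of at least .5 SD units in the difference in the z-scores". The method is to "compute the mean difference and a 90% confidence interval based on a t-test. This results in an equivalence test with an alpha=0.05", and the decision rule reads: "If the entirety of bounds of the 90% confidence interval are between (-.5SD, .5SD), then the two assessments will be considered equivalent". The calculation is then repeated within each referral diagnosis.

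The endpoint is set in section C (Outcome Measures): "Z-scores will be calculated based on age-referenced normative data for each cognitive test", averaged within each of four domains. The Core Battery list in section B places two tests under Memory (a verbal list-learning test and figure recall). It also includes several short tests: a 15-item naming test, a short-form line-orientation test, an abbreviated vocabulary test and a calculation screen.

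On the population, section A says: "The typical and atypical AD groups will range in severity from MCI to mild dementia". Moderate to severe dementia is excluded, and the typical group is defined by a memory-predominant presentation.

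Section E (Potential Scientific Problems) covers practice effects and test-retest reliability. It grants that the 0.5 SD domain margin may not suit individual tests, and says only that test-specific comparisons will be considered. Floor effects, ceiling effects, counts of patients at a score limit and censored-data methods appear nowhere.

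**The concern.** A patient who scores at the floor of a test face to face cannot be recorded as scoring lower by video. If video lowers performance, the part of the drop beyond the limit is lost. The mean difference moves toward zero and the SD of the differences shrinks. In a superiority trial this costs power. In an equivalence trial both changes push toward success. The ceiling is the mirror image: if the FF score is already at the maximum, part of a true drop by video can be hidden.

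Two conclusions are exposed. TeleNP could be called equivalent for a domain partly because the tests could not register the deficit. And if limits are reached more often in one referral group than in the other, the stratified results used to answer Aim 1b could differ for that reason alone.

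**Working it through.** **Inputs from the document.** Randomised-order cross-over ("Order of modality will be randomized at baseline using a computerized process through REDCap"), so the unit is the paired difference; n=80 overall and 40 per referral group ("Neurologist-referred patients with typical (i.e., memory-predominant; n=40) and atypical (i.e., complex and/or non-memory predominant; n=40) presentations"); margin 0.5 SD; 90% t interval.

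**Inputs assumed, because the document gives none.** Score SD 1; SD of paired differences 0.75; underlying TeleNP shift -0.5; floor at z = -3; half of the stable between-patient variance shared between tests in a domain; cohort mean -1.0, -1.5 or -2.0. Section F uses -1.5 and -2.0 as example impairment levels for an individual, not as expected cohort means. Differences are TeleNP minus FF; the margin is symmetric.

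**Step 1. The plan's own figure.** With no floor and a true mean of -0.5, equivalence requires mean - t × SE > -0.5, which happens with probability 0.05. Exact calculation gives 0.0500 at n=80 and at n=40, for difference SDs of 0.5, 0.7 and 1.0. The stated alpha reproduces.

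**Step 2. Attenuation for one floored test.** For a score with mean μ, SD 1 and floor f, let a = f - μ. The recorded mean is f·Φ(a) + μ·(1 - Φ(a)) + φ(a).

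- FF, μ = -2.0: a = -1, so -3(0.1587) - 2(0.8413) + 0.2420 = -1.917.
- TeleNP, μ = -2.5: a = -0.5, so -3(0.3085) - 2.5(0.6915) + 0.3521 = -2.302.
- Recorded difference: -2.302 + 1.917 = -0.385, not -0.5. Shares at floor: 16% (FF) and 31% (TeleNP).
- At μ = -1.5 the recorded difference is -0.446, with 7% and 16% at floor. At μ = -1.0 it is -0.479, with 2% and 7%.

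**Step 3. From attenuation to pass rate.** At mean -2.0 the simulated SD of differences falls from 0.75 to 0.645. With n=80, SE = 0.645/√80 = 0.0721 and t × SE = 1.664 × 0.0721 = 0.120. Equivalence needs a mean above -0.380, against an expected -0.385. The pass probability is about 0.47, and simulation gives 47% to 48%.

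**Step 4. The actual endpoint, a domain mean.** Simulated false equivalence (20,000 trials per cell) at an underlying shift of -0.5:

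| Mean | n | One test alone | 1 of 2 floored | 2 of 2 floored | 1 of 4 floored | 1 of 6 floored |
|---|---|---|---|---|---|---|
| -1.0 | 80 | 8% | 7% | 10% | 7% | 6% |
| -1.0 | 40 | 7% | 7% | 8% | 6% | 6% |
| -1.5 | 80 | 17% | 12% | 25% | 9% | 8% |
| -1.5 | 40 | 13% | 9% | 17% | 7% | 7% |
| -2.0 | 80 | 48% | 27% | 71% | 16% | 14% |
| -2.0 | 40 | 30% | 18% | 46% | 13% | 11% |

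Averaging with unaffected tests dilutes the bias. If both tests floor, the bias is the same as for one test while the SE is smaller, so the rate rises.

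**Step 5. Error on the recorded scale.** When the underlying shift is set so that the recorded mean difference is itself -0.5, the t interval passes 4.9% to 5.7% of the time in the -1.5 and -2.0 settings. A separate run (SD 1, correlation 0.75) gave 5.8% to 6.1% with 20% of FF scores at floor, and 6.7% to 7.4% with 40%.

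**Step 6. Unequal floors by referral group.** Take n=40 per group, a two-test domain, the same underlying shift of -0.5 in both groups, and correlation 0.75 between visits. If 30% of FF scores are at floor in one group and 10% in the other, the pass rates are 91% and 28% when both tests floor, and 39% and 13% when one does.

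**The case against.** The strongest reply is that the plan's null concerns recorded z-scores, and Step 5 shows that the interval nearly keeps its level there. That stands. A reader might infer that the 0.05 in the SAP is wrong; it is not. The rates in Step 4 measure how often an underlying 0.5 SD effect is missed because the scores cannot carry it. They still matter, because Aim 1 is presented as a test of validity and its result will be read as a statement about the modality.

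It can also be said that a patient recorded at -3 is already below both severity thresholds behind the margin, so a further drop would change no category. That is fair for an individual, but it does not repair the mean difference on which the claim is based.

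Other points limit the size, and they stand:

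- Excluding moderate to severe dementia limits flooring, and every floor share here is assumed.
- The endpoint averages several tests. This helps least where few tests are listed, as for Memory.
- The trial is a pilot of preliminary validity.

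Three further inferences go beyond the document. Patients at a limit are not unable to show any difference: at the floor they can still show a rise, and only when both scores sit at the same limit is the difference exactly zero. Memory floors need not be more common in the typical group, because the groups are defined by predominance rather than depth of impairment and the atypical group includes complex cases. And Aim 1b has no formal between-group test that could be biased; it has repeated stratified intervals.

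**Conclusion.** The concern holds as an unaddressed attenuation that favours equivalence, not as a failed alpha. In a two-test domain at n=80, an underlying 0.5 SD deficit would be called equivalent about 12% to 25% of the time at a mean of -1.5, and about 27% to 71% at -2.0; the lower figure is for one test floored and the upper for both. At n=40 the ranges are about 9% to 17% and 18% to 46%. If few patients are at a limit, the rate is about 5% to 10% and the issue is minor; it is also smaller when only one of many tests in a domain is affected.

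All of this rests on the assumed floor at -3, the SDs, the shared variance and normal underlying scores. The document cannot show where the trial falls in these ranges; a count of scores at the limits would. Differing stratified results for Aim 1b are likewise a possibility that depends on unequal floor shares, not something the document establishes.

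**What to change.** Keep the 90% t interval on the domain mean as the primary analysis, and add three items to section F:

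1. For each Core test, by modality and referral group, report the share of patients at the lowest and at the highest obtainable score. If the scoring calculator caps z-scores at the end of a norm table, say so and count capped scores as at the limit.
2. For any domain containing a test above a set share at a limit in either modality (10%, for example), prespecify a sensitivity analysis of the domain difference. Use either a censored (Tobit-type) paired model or a domain mean that omits the affected tests. State how per-test estimates combine into a domain interval, for instance by averaging them and bootstrapping whole patients (not checked here). Omission works poorly for Memory, where two listed tests leave one or none.
3. If the sensitivity interval is not inside ±0.5 SD, describe the equivalence claim for that domain or stratum as limited by floor or ceiling.

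The censored model was checked on a single normal score (SD 1, correlation 0.75, 1,000 trials per setting). With 10%, 20% and 40% of FF scores at floor, false equivalence at n=80 fell from 29%, 68% and 99.5% to 5%, 5% and 6%. At n=40 it fell from 17%, 41% and 90% to 4%, 5% and 6%. In a smaller check (300 trials, mean -2, floor -3), the pass rate at a true difference of zero was 100% at n=80 and 98% at n=40. Short tests with few score levels were not checked.

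The cost is some SAP wording and a little more analysis of data already collected, with a normality assumption and a somewhat wider interval in the sensitivity analysis only.

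### Aim 1 calls TeleNP and FF equivalent from the mean paired difference alone, which bounds average modality bias; no measure of patient-level score agreement is committed

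*Combined protocol and SAP*

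**What the plan says.** Section I states Aim 1 as: "Determine the validity of home-based video administration of neuropsychological tests (TeleNP) for assessing AD". Section IV.C (Outcome Measures, Aim 1) gives its goal as to "test the concurrent validity of cognitive measures across testing modalities". The outcome is a mean normative z-score for each of four domains, obtained in both modalities from 80 patients (40 typical, 40 atypical referrals).

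Section IV.F commits to one decision rule. The FF–TeleNP difference is computed for each patient, and a t-based 90% interval is formed for the mean difference. Then: "If the entirety of bounds of the 90% confidence interval are between (-.5SD, .5SD), then the two assessments will be considered equivalent". The same computation is repeated by referral diagnosis, sex and race/ethnicity. On the margin, the SAP says: "We elected a .5 SD margin as an initial threshold for a clinically meaningful difference". Its reason concerns single patients: "once an individual reaches a level deemed to be clinically significant impairment", a shift of half an SD moves that person by one severity category.

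Section IV.E (Statistical Analysis Framework) partly recognises the issue. It mentions reliable change indices, warns that half an SD in a domain mean may not reflect a meaningful difference in individual test scores, and says that a test-specific check against published reliability will be considered. Section IV.G lists test-specific differences in validity among the knowledge to be gained but names no analysis.

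**The concern.** A mean difference near zero can arise because each patient scores alike in both modalities, or because large differences in opposite directions cancel. The Aim 1 rule separates these cases only indirectly, since scatter widens the interval. The individual-level argument for 0.5 SD reasonably supports a cap on systematic bias, but it puts no bound on how far one patient's two scores may differ.

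Under an aim about validity, a pass would be reported as equivalence of the two assessments when the rule supports only a small average bias. The pilot is meant to prepare a definitive trial, and the planners of that trial would need to know how closely individual scores agree.

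**Working it through.** **Inputs from the documents.** n=80 pooled and 40 per referral stratum; 90% t-interval; margin ±0.5 SD; stated alpha 0.05; visits 4–6 weeks apart (maximum 90 days); practice effects of at most 0.10–0.15 (Section IV.E).

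**Assumptions.** The documents give neither the score SD nor the FF–TeleNP correlation r, so ranges are shown. Scores are normal with equal SD in both modalities, the true mean difference is 0, and the margin is read as 0.5 z-units.

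**1. The plan's own figure.** A 90% interval leaves (1 − 0.90)/2 = 0.05 in each tail. With the true mean difference set at 0.5, the rule passes with probability 0.050. The stated alpha is right.

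**2. How much scatter the rule tolerates.** The half-width is t(0.95, n−1) × SDdiff/√n. With an observed mean difference of 0, the rule passes while SDdiff < 0.5√n/t:
- n=80: 0.5 × 8.944/1.664 = 2.69
- n=40: 0.5 × 6.325/1.685 = 1.88

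For comparison, SDdiff = SD√(2(1−r)). At SD 1 it is 0.632, 1.000 and 1.414 for r = 0.8, 0.5 and 0. The share of patients whose two scores differ by at least 0.5 is 2(1 − Φ(0.5/SDdiff)), which gives 43%, 62% and 72%.

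**3. Probability that the rule passes**, integrating over the chi-square distribution of the sample variance:

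| SD 1 | r=0.8 | r=0.5 | r=0 |
|---|---|---|---|
| Pooled, n=80 | about 100% | 99.5% | 86% |
| One stratum, n=40 | 99.9% | 86% | 42% |
| Both strata pass | 99.8% | 73% | 18% |

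The last row is the square of the row above it (unrounded), because the strata contain different patients.

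The result depends on the score SD. For one n=40 stratum, r=0.8 against r=0.5:
- SD 0.8: 100% against 97%
- SD 1.25: 98% against 60%
- SD 1.5: 90% against 33%

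So the strata do penalise poor tracking when the SD is 1 or more. The pooled test penalises it weakly (n=80, SD 1.5: 99.8% against 81%).

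**4. The other reading of the margin.** If the margin means the SD of the differences, the half-width is 0.186 SDdiff (n=80) or 0.266 SDdiff (n=40) at any level of agreement. The rule would then not respond to scatter at all, which strengthens the point, but the table above would not apply.

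**5. What agreement statistics would show at SD 1.** The limits of agreement are ±1.96 × SDdiff. The 95% CI half-width of each limit is t(0.975, n−1) × SDdiff × √(1/n + 1.96²/(2(n−1))), that is 0.382 SDdiff at n=80 and 0.551 SDdiff at n=40. ICC intervals are medians over 3,000 simulated samples.

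| | r=0.8 | r=0.5 |
|---|---|---|
| Limits of agreement | ±1.24 | ±1.96 |
| CI of each limit, n=80 | ±0.24 | ±0.38 |
| CI of each limit, n=40 | ±0.35 | ±0.55 |
| ICC 95% CI, n=80 | 0.70–0.87 | 0.32–0.65 |
| ICC 95% CI, n=40 | 0.65–0.89 | 0.23–0.70 |

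The two cases separate at n=80 and overlap at n=40.

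**6. Two cautions on reading them.** A practice effect of 0.15 with balanced order raises SDdiff to √(0.40 + 0.15²) = 0.650 at r=0.8 and √(1 + 0.15²) = 1.011 at r=0.5, a small part of the scatter if that figure holds. ICC also depends on spread: with a per-session error variance of 0.2, 1 − 0.2/SD² is 0.69, 0.80, 0.87 and 0.91 at SD 0.8, 1, 1.25 and 1.5.

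**The case against.** The best defence is that equivalence is a defined term here. The null hypothesis is stated for an average difference, Section IV.E says that equivalence is judged on mean domain scores, and Aim 1a can be read as a question about the group. The authors also disclose the individual-level limitation, call the margin initial and the validity preliminary, and point to a reliability-based check. That explains the rule. It does not qualify the conclusion sentence, and concurrent validity is wider than mean bias. The check in Section IV.E is optional, lies outside the SAP and names no agreement statistic.

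A second argument is that Aim 2 supplies patient-level concordance through its 3x3 table of TeleNP against FF diagnosis. The table is paired and useful, but it concerns diagnoses rather than scores, and its decision rule compares marginal proportions. It narrows the gap without closing it.

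The third argument is about the remedy, and much of it stands. Limits of agreement and ICC mix modality with retest noise, alternate forms, elapsed time and order. Without a repeat FF visit, excess scatter cannot be assigned to modality with certainty. At n=40 the estimates are imprecise, whereas the existing rule does react to scatter in the strata. The agreement figures should therefore be descriptive and carry these caveats. The true r is also unknown, and nothing in the documents makes a low value likely.

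**Conclusion.** The concern holds. The interval is a valid 0.05-level test that mean modality bias is below 0.5 SD, and a pass supports that statement only. Its protection against poor patient-level tracking is partial: weak in the pooled test, stronger in the n=40 strata, and dependent on a score SD that the documents do not give. The pass rates rest on normal scores, zero mean bias and a margin in z-units. The qualitative conclusion does not depend on the particular values of SD and r, though the size does.

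This should be fixed. The pilot framing limits the harm, and the gap lies in the analysis and in what may be concluded, not in the design.

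**What to change.** 1. In Section IV.F, limit the conclusion from the 90% interval to *mean modality bias is below 0.5 SD*, pooled and by stratum.
2. Pre-specify for each domain, descriptively and with no pass/fail threshold, the 95% limits of agreement and a two-way, single-measure, absolute-agreement ICC, with 95% CIs for each limit and for the ICC.
3. State beside them that the scatter includes retest noise, elapsed time, alternate forms and practice or order effects; that ICC depends on between-patient spread and may differ between strata for that reason alone; and that without a repeat FF visit excess scatter cannot be attributed to modality with certainty.
4. Optionally, make the Section IV.E check firm. Where a published retest reliability r_tt exists, compare the observed SD of differences with SD√(2(1−r_tt)), noting that r_tt may come from another population or interval.

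A separate wording correction, which adds no weight to this point: the alternative hypothesis is given as the mean "difference in the z-scores is zero", and should read as an absolute mean difference below 0.5 SD.

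The cost is SAP wording and a few lines of analysis, with no added visits or patients. The results will look less favourable, because ordinary retest noise alone gives limits of about ±1.24 at r=0.8 and SD 1. The n=40 stratum estimates will not reliably separate r=0.8 from r=0.5.
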